In addition, results of randomized Phase II study have been published (Tefferi, 2009). In a phase II randomized, multicenter, double-blind, adaptive design study, four treatment arms were evaluated: pomalidomide (2 mg/day) + placebo, pomalidomide (2 mg/day) + prednisone, pomalidomide (0.5 mg/day) + prednisone, and prednisone + placebo. Pomalidomide was administered for up to twelve 28-day treatment cycles. Prednisone (30 mg/day) was given in a tapering dose schedule during the first three cycles. Response was assessed by International Working Group criteria. Eighty four patients with MMMassociated anemia were randomly assigned to the above-listed treatment arms: 22, 19, 22 and 21, respectively. All active patients have completed six cycles of treatment. Response in anemia was documented in 20 patients, including 15 who became transfusionindependent. Response rates in the four treatment arms were 23%, 16%, 36% and 19%. The corresponding figures for patients receiving ≥ 3 cycles of treatment (n=62) were 38%, 23%, 40% and 25%. Response to pomalidomide ± prednisone was durable (range 3.2-16.9+ months) and significantly better in the absence of leukocytosis (37% vs. 8%; p=0.01); JAK2V617F or cytogenetic status did not affect response. Grade ≥ 3 toxicities were infrequent and included (in each treatment arm) neutropenia (9%-16%-5%-5%), thrombocytopenia (14%-16%-9%-5%) and thrombosis (9%-5%-0%-0%). Pomalidomide therapy at $0.5 \pm an$ abbreviated course of prednisone is well tolerated in patients with myelofibrosis and active in the treatment of anemia.

Finally, 20 patients have been accrued into current study so far, with starting dose of 3mg/day. After median follow up of 2 months, most patients had to interrupt the therapy due to side effects: 13 patients experienced myelosuppression, 3 had rash/swelling. The study accrual has been put on hold, pending modification of the dose to 0.5mg/day (given continuously).

ADDENDUM 3/30/11:

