3. INVESTIGATIONAL PLAN

3.1. Overall design

CC-4047 is a phase 2, prospective, open-label study to determine the efficacy and safety of CC-4047 at a 0.5 mg dose, in combination with prednisone, to study further in subjects with primary, post polycythemia vera, or post essential thrombocythemia myelofibrosis

Screening:

Potential subjects will enter screening and be evaluated for the inclusion and exclusion criteria for the Treatment Period of this study. The screening period will not last more than 28 days. The assessments and procedures that will be performed during screening are outlined in Appendix M: Schedule of Events. Screening assessments will include an informed consent, medical history, review of prior medications, complete physical exam, ECOG performance status assessment, complete blood count (CBC) with differential, serum chemistries, urinalysis, thyroid function tests, 12-lead ECG, bone marrow biopsy and aspirate to confirm diagnosis and for standard cytogenetics, JAK2 mutation (by quantitative polymerase chain reaction [PCR], and PCR or fluorescent in situ hybridization (FISH) for bcr/abl, spleen and/or liver (if spleen is absent) measurements, and QoL Assessments.

Females of reproductive potential¹ must adhere to the scheduled pregnancy testing as required in the POMALYST REMSTM program. All study participants must be registered into the mandatory POMALYST REMSTM program, and be willing and able to comply with the requirements of the POMALYST REMSTM program.

Before starting study drug:

Subjects must follow pregnancy testing requirements as outlined in the POMALYST REMS TM program.

Treatment Period:

Subjects meeting all inclusion and exclusion criteria will receive 0.5mg CC-4047. Prednisone will be given during first 3 cycles of therapy. It will be dosed orally at the dose of 30 mg/day during cycle 1, 15 mg/day during cycle 2, and 15 mg every other day during cycle 3, and then it will be discontinued. Prednisone will be used from commercially available supplies.

Subjects will remain on study treatment in the Treatment Period in the absence of disease progression or toxicity warranting discontinuation of therapy. Twenty-eight days is considered one cycle of therapy. Subjects may be taken off study at 6 months if there is no response, however, they should continue to be followed until disease progression or initiation of an alternate therapy.

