3.9. Follow-Up

Subjects who discontinue treatment for any reason, will be followed every three months until disease progression or initiation of alternate therapy. At treatment discontinuation, subjects will undergo a safety assessment approximately 28 days post the last dose of study drug. In addition, off study evaluations per the Schedule of Assessments, Appendix M will be done.

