5.3.3. Analysis Plan

Primary Endpoint

The observed response rate over the first 6 cycles of therapy at 0.5mg/day will be estimated by the number of responses (confirmed CR, PR or CI) over the first 6 cycles divided by the total number of evaluable subjects. Confidence intervals for the true response rates will be calculated according to the approach of Duffy and Santner.

Secondary Endpoints

Duration of response: duration of response is defined as the date at which the subject's objective status is first noted to be a CR, PR or CI to the date progression is documented (if one has occurred) or to the date of last follow-up (for those subjects who have not progressed).

Time to response: The time to response is defined as the time from study registration to the first date at which the subject's objective status was classified as a response (CR, PR or CI). In subjects who do not achieve a response, time to response will be censored at the subject's last evaluation date. The distribution for each of these event-time variables (duration of response and time to response) will be estimated by Kaplan-Meier curves.

Best overall response as determined by the International Working Group Criteria over the first 12 cycles of study treatment: will be estimated by the number of responses (confirmed CR, PR or CI) over the first 12 cycles divided by the total number of evaluable subjects. Confidence intervals for the true response rates will be calculated according to the approach of Duffy and Santner.

Cytogenetic responses and molecular response: cytogenetic responses and molecular responses will be summarized as well as evaluated graphically. Correlations among clinical responses and laboratory variables will be explored using a Wilcoxon/Kruskal-Wallis test for ordered contingency tables. Mutation status will be explored in relation to clinical outcome (response) using Fisher's exact test.

Quality of Life (QOL) assessments: For each of the QOL assessment components, changes from baseline to each of the follow-up time points will be reported. The change will be compared between two subgroups: subjects who response to the treatment and subjects who do not response. Normality testing via the Shapiro-Wilk procedure will determine whether or not parametric or nonparametric procedures will from the basis for analysis (two-sample t-test, Wilcoxon rank sum test).

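### Secondary endpoints, minor: the Kaplan-Meier curve for time to response censors competing events and can overstate response, and duration of response does not count death

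*Combined protocol and SAP*

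**What the plan says.** Section 5.3.3 (Secondary Endpoints) measures time to response from registration to the first CR, PR or CI. For everyone else the rule is: "In subjects who do not achieve a response, time to response will be censored at the" last evaluation date. It makes no distinction by why that evaluation was the last.

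Duration of response runs from first response to documented progression, "or to the date of last follow-up (for those subjects who have not progressed"). The distributions of both variables "will be estimated by Kaplan-Meier curves".

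Two other sections determine when evaluation stops. Section 3.9 says that subjects who come off treatment "will be followed every three months until disease progression or initiation of alternate therapy". Section 3.1 says of non-responders taken off at 6 months that "they should continue to be followed until disease progression or initiation of an alternate therapy".

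The same section 5.3.3 also reports response over 6 and over 12 cycles as responders divided by all evaluable subjects, with confidence intervals. Nothing in the text reviewed mentions competing events or says how death or alternate therapy enters either curve. The IWG definition of progression is not reproduced there, and the schedule of assessments (Appendix M) was not part of it.

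**The concern.** Kaplan-Meier treats a censored subject as someone who could still respond at the same rate as those who remain at risk. That is reasonable for a subject lost to follow-up or still under evaluation at data cut-off. It is not reasonable for a non-responder who has died, progressed or moved to another therapy. The method shares that subject's probability among those who remain, so the estimated probability of response is too high.

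For duration, a responder who dies without documented progression is counted as having a response that was still continuing when last seen. Both effects favour the treatment. What is at stake is the accuracy of two descriptive curves, and whether the time-to-response curve agrees with the response proportions printed beside it.

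**Working it through.** **What the plan states.** It gives no figure for either curve. Its stated figures concern the two-stage rule (sections 5.3.2, 5.5 and 5.6): stop with 1 or fewer successes in 20, and call the regimen promising with 4 or more in 37. With X1 from 20 subjects and X2 from the next 17, P(promising) = Σ over x = 2 to 20 of P(X1 = x) × P(X2 ≥ 4 − x). This gives 0.0898 at a true rate of 5% and 0.9100 at 20% (stated 0.09 and 0.91). The probability of stopping at stage 1 is 0.7358 and 0.0692 (stated 0.74 and 0.07). These reproduce, and neither curve enters them.

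**Direction.** Let h_R be the hazard of response. The cumulative incidence is the sum of S(t−)·h_R, where S is the probability of being free of both response and competing events. One minus Kaplan-Meier is the sum of S_R(t−)·h_R, where S_R removes responses only. Since S ≤ S_R at every time, 1−KM is never below the cumulative incidence. The two are equal if no competing event precedes a response.

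**Scale of exits (assumption).** The only guide is the earlier randomised study in section 1.2, Addendum 11/10/09.
- Patients were "randomly assigned to the above-listed treatment arms: 22, 19, 22 and 21, respectively".
- "Response rates in the four treatment arms were 23%, 16%, 36% and 19" per cent, which gives 5/22, 3/19, 8/22 and 4/21, or 20 responders as stated there.
- Among those with at least 3 "cycles of treatment (n=62) were 38%, 23%, 40% and 25" per cent. If all responders are in this group, these are 5/13, 3/13, 8/20 and 4/16, and 13 + 13 + 20 + 16 = 62 as stated.
- In the 0.5 mg plus prednisone arm, 22 − 20 = 2 of 22 (9.1%) therefore had fewer than 3 cycles. 37 × 0.091 = 3.4, so I use 3 to 4.

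These are exits from treatment, with no reason given. Treating them as competing events is an assumption.

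**Response times (assumption).** Seven responders at 2, 3, 3, 4, 5, 6 and 9 months. The median of 4 and the range of 2 to 9 are from the phase 1 update in the same addendum; the values between are mine. In 28-day cycles these are 2.17, 3.26, 3.26, 4.35, 5.44, 6.52 and 9.78.

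**Results for 37 subjects, exits evenly spaced in cycles 1 to 3:**

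| | 6 cycles | 12 cycles |
|---|---|---|
| Proportion (= cumulative incidence) | 5/37 = 13.5% | 7/37 = 18.9% |
| 1−KM, 3 exits | 1 − (34/35)(29/33) = 14.6% | 1 − (34/35)(27/33) = 20.5% |
| 1−KM, 4 exits | 1 − (33/34)(28/32) = 15.1% | 1 − (33/34)(26/32) = 21.1% |
| Excess, points | 1.1 to 1.6 | 1.6 to 2.2 |

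The binomial standard errors are √(0.135 × 0.865/37) = 5.6 points and √(0.189 × 0.811/37) = 6.4 points, so the excess is at most about a third of one standard error.

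**Sensitivity.**
- Same exits spread over 12 cycles: excess 0.3 to 0.4 points at 6 cycles and 0.8 to 0.9 at 12.
- No exits: zero.
- No early exits, but 8 or 16 of the 32 subjects without a response at 6 cycles progress or start other therapy just afterwards (assumed): 1 − (32/37)(22/24) = 20.7% or 1 − (32/37)(14/16) = 24.3% at 12 cycles, against 18.9%.
- Constant hazards, true response 20%, assumed competing exits 10% or 25%: 1−KM = 1 − exp{ln(1 − 0.20 − c) × 0.20/(0.20 + c)} = 21.2% or 23.3%.

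**Duration.** No calculation is possible. The documents give neither the rate of death without documented progression among responders nor a duration estimate for this regimen.

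**The case against.** The strongest reply is that the quantity of interest is already reported. The 6- and 12-cycle proportions use all evaluable subjects and, with complete follow-up, are the cumulative incidence at those horizons. Exact agreement with the curve was never assured: the curve starts at registration, the proportions count cycles, and section 3.6.2 allows cycles to be delayed. This stands, and is why the point is minor. It does not make the curve between and beyond those horizons correct.

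A second reply is that leaving treatment is not leaving evaluation, since sections 3.1 and 3.9 keep such subjects in follow-up. This also stands. A reader might take 2 of 22 as the rate of competing events, but the documents do not support that, so the 1 to 2 points are illustrative only. The response times are likewise largely assumed, and five of the seven responses in the source study came only after dose reduction.

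A reader might also infer a much larger bias. With true response of 36% and 50% competing exits, constant hazards give 56.1%, about 20 points too high. No exit rate of that kind appears in the documents.

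Finally, a reader might derive an overstatement in months from the 15-month response duration and the survival rates in section 1. That does not work. The 15 months belong to a different drug with prednisone, and responses were ongoing in 10 of 12 responders. The survival rates run from diagnosis, and the share of deaths without documented progression is unknown.

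**Conclusion.** The point holds as a minor one, on two secondary, descriptive endpoints. The censoring rule for time to response, read with the follow-up rules, makes 1−KM equal to or higher than the cumulative incidence. The direction follows from the estimator. The size rests on assumed exits and response times: about 1 to 2 points with 3 to 4 early competing exits among 37, more if more non-responders leave evaluation through such events, and zero if none do.

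Duration of response is overstated if a responder dies without documented progression. This part is conditional: it falls away if the IWG definition of progression includes death. No magnitude can be given.

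A reader might infer that the activity conclusion is at risk. It is not: the primary endpoint, the requirement of at least 2 of 20 at the interim and 4 of 37 at the end, alpha of 0.09 and power of 0.91 use neither curve.

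**What to change.** In section 5.3.3:
- Estimate time to response by the cumulative incidence function (Aalen-Johansen), with death, progression and start of alternate therapy before response as competing events. Censor only subjects who are lost to follow-up, have withdrawn, or are still under evaluation at data cut-off.
- Define duration of response as first response to progression or death from any cause, whichever comes first, censored at the last response assessment.
- State one rule for responders who start alternate therapy (censored at its start, or counted as an event), with a sensitivity analysis under the other rule.

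The cost is a few sentences and a standard routine. Dates of death and of starting alternate therapy must be recorded; section 3.9 already uses the start of alternate therapy to end follow-up. The curves may look slightly less favourable. Sample size and decision rules need no change.

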5.3 Statistical Methodology

5.3.1. Primary Endpoint

The primary endpoint of this trial is best overall response. An evaluable subject will be classified as a treatment success for the primary endpoint if the subject's best overall response is CR, PR or CI (Clinical Improvement) as determined by International Working Group Criteria over the first 6 cycles of study treatment at 0.5mg/day dose. The largest success proportion where the proposed treatment regimen would be considered unpromising in this population is 5%, representing the probability of a response by chance. The smallest success proportion that would warrant further subsequent studies with the proposed treatment regimen in this subject population is 20%.

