5.3.2. Study Design

Subjects receiving CC-4047 alone, and the new study cohort of patients receiving CC-4047 and prednisone in combination will be evaluated using the same statistical design: a two stage design with one interim analysis will be used to permit early reporting of efficacy results if there is strong evidence that the study regimen is inactive. 37 evaluable subjects will be accrued onto this study unless undue toxicity is encountered. We anticipate accruing an additional 10-20% of subjects to account for ineligibility or cancellation; i.e. we may accrue as many as 70 subjects to this study. Subjects who have been taken off study due to toxicity related to high dose pomalidomide (i.e. those who started therapy with 3mg/day) will be replaced with new patients that will start therapy with 0.5mg/day), so that the goals of the study can be accomplished.

• Decision Rule: If 3 or fewer treatment successes are observed after all 37 evaluable subjects have been followed for at least 6 cycles, we will conclude that the treatment is insufficiently active in this subject population. If 4 or more treatment successes are observed, then this will be considered adequate evidence of promising activity, and the treatment may be recommended for further testing in subsequent studies.

- Over accrual: if more than the target number of subjects are accrued, the additional subjects will not be used to evaluate the stopping rule or used in any decision making process. However, they will be included in final point estimates and confidence intervals.
- Study duration: The anticipated accrual rate for this group of subjects is approximately 3 subjects per month. It will take approximately 14 months to accrue 37 evaluable subjects. The analysis can begin as soon as the 37th evaluable subject has been observed for 6 cycles (168 days), i.e., approximately 20 months after the trial opens.

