5.5 Interim analyses

An interim analysis will be performed after the first 20 evaluable subjects have been observed for at least 6 cycles. If 1 or fewer treatment successes are observed in these 20 subjects, this treatment regimen will be considered inactive in this population and accrual will be terminated. If 2 or more treatment successes are observed in these 20 subjects, decisions about activity must await the final analysis. Enrollment into the study will continue while waiting for the 20th eligible subject to complete at least 6 cycles of treatment. These additional subjects will not be used to evaluate the interim stopping rule.

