5.6. Sample size and power considerations

Assuming that the number of successes is binomially distributed, this decision rule has a significance level of 0.09; i.e., there is a 9% chance of finding the drug to be effective when it truly is not. The probability of declaring that this regimen warrants further studies (i.e. statistical power) under various success proportions and the probability of stopping after the first stage can be tabulated as a function of the true success proportion as shown in the following table:

If the true success proportion is	0.05	0.10	0.15	0.20	0.25
then the probability of declaring that the	0.09	0.44	0.75	0.91	0.97

regimen warrants further studies is					
And the probability of stopping at stage I	0.74	0.39	0.18	0.07	0.02
is:					

In particular, this decision rule has 91% power to detect an effective treatment given that the true response rate is at least 20% using this treatment. If the true success rate is 5%, the chance of stopping early at the first stage is 0.74 and the chance of concluding that the treatment is active is 0.09. If the true success rate is 20%, the chance of stopping early at the first stage is 0.07 and the chance of concluding that the treatment is active is 0.91 (power).

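### The 12-cycle response rate is assigned a two-stage Duffy-Santner interval although stopping depends only on the 6-cycle count, so the interval is undefined after some early stops

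*Combined protocol and SAP*

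**What the plan says.** Section 5.3.1 defines a success as CR, PR or CI "as determined by International Working Group Criteria over the first 6 cycles of study treatment at 0.5mg/day dose". Both decision rules count that event. Section 5.5 sets the first look: "An interim analysis will be performed after the first 20 evaluable subjects have been observed for at least 6 cycles". It continues: "If 1 or fewer treatment successes are observed in these 20 subjects, this treatment regimen will be considered inactive", and accrual then ends. Section 5.3.2 sets the final rule: "If 3 or fewer treatment successes are observed after all 37 evaluable subjects have been followed for at least 6 cycles", the treatment is judged insufficiently active; 4 or more successes count as promising. The same design serves the CC-4047-alone cohort and the combination cohort.

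Section 5.3.3 gives the 6-cycle rate a Duffy-Santner interval. It then does the same for the secondary endpoint, the responses "over the first 12 cycles divided by the total number of evaluable subjects. Confidence intervals for the true response rates will be calculated" by that approach. It describes no adaptation, states no confidence level, and the method is not in the reference list.

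Two further provisions matter. Enrolment continues while the 20th subject completes 6 cycles (5.5). Subjects beyond the target are kept out of the decisions but enter the final point estimates and confidence intervals (5.3.2).

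**The concern.** An interval built for a two-stage binomial design orders the outcomes that the stopping rule can produce, and gives each its probability under that rule. That requires the count being estimated to be the count that decided whether the trial continued. This is true of the 6-cycle count. It is not true of the 12-cycle count, which plays no part in stopping and can only equal or exceed the 6-cycle count.

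Two things follow. A cohort stopped at 20 with 0 or 1 success at 6 cycles may have 2 or more responders by 12 cycles, an outcome for which the method has no place. In a cohort that goes on to 37, a limit can be read off, but the stage probabilities behind it belong to the 6-cycle rate.

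What is at stake is a pre-specified interval for a listed secondary endpoint: in some early-stopped trials it could not be reported as planned, and in the others it would not be the procedure its name implies.

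**Working it through.** **Inputs from the plan.** Stage 1: 20 subjects, stop at 1 or fewer (5.5). Total: 37, promising at 4 or more (5.3.2). Unpromising rate 5%, target rate 20% (5.3.1). Accrual 3 per month (5.3.2). Six cycles are 168 days (2.2.1).

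**Assumptions.** The documents give no 12-cycle rate, so the late gain g = p12 − p6 is set at 0, 2, 5 and 10 percentage points. Subjects respond independently. Duffy-Santner is taken to use the two-stage sample space; the plan does not describe it.

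**Step 1: the plan's own figures.** P(stop) = P(Bin(20, p) ≤ 1). P(promising) = Σ over x ≥ 2 of P(Bin(20, p) = x) · P(Bin(17, p) ≥ 4 − x).

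| p | 0.05 | 0.10 | 0.15 | 0.20 | 0.25 |
|---|---|---|---|---|---|
| P(stop) | 0.7358 | 0.3917 | 0.1756 | 0.0692 | 0.0243 |
| P(promising) | 0.0898 | 0.4392 | 0.7512 | 0.9100 | 0.9713 |

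These agree with the table in 5.6, where "this decision rule has a significance level of 0.09" and power is 0.91.

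**Step 2: the sample space.** Under this rule the possible outcomes are 0-1 of 20, or 2-37 of 37. The missing outcomes are 2 or more of 20.

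**Step 3: how often the 12-cycle count lands there.** The chance that a 6-cycle non-responder responds in cycles 7-12 is q = g/(1 − p6). Then

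P(undefined) = P(X6 = 0) · P(Bin(20, q) ≥ 2) + P(X6 = 1) · P(Bin(19, q) ≥ 1).

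For p6 = 0.05 and g = 0.05:
- q = 0.05/0.95 = 0.0526
- P(X6 = 0) = 0.95^20 = 0.3585, and P(Bin(20, q) ≥ 2) = 0.2840; product 0.1018
- P(X6 = 1) = 20 · 0.05 · 0.95^19 = 0.3774, and P(Bin(19, q) ≥ 1) = 0.6420; product 0.2423
- sum 0.344

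| 6-cycle rate | g = 0 | g = 2 | g = 5 | g = 10 | ceiling, P(stop) |
|---|---|---|---|---|---|
| 5% | 0 | 14.9% | 34.4% | 56.0% | 73.6% |
| 10% | 0 | 10.3% | 21.6% | 32.3% | 39.2% |
| 15% | 0 | 5.3% | 10.6% | 15.1% | 17.6% |
| 20% | 0 | 2.3% | 4.5% | 6.2% | 6.9% |
| 36% | 0 | <0.2% | <0.2% | <0.2% | 0.16% |

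The last row uses the anemia response rate reported for the low-dose combination in section 1.2. The CC-4047-alone cohort had 3 successes in 20 at its interim (section 1.2), so it passed stage 1 and cannot enter the undefined region.

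**Step 4: the number analysed.** Step 3 takes 20 subjects at an early stop. During the wait for the 20th subject, 168 days (5.52 months) at 3 per month adds 16.6 subjects, so about 37 are enrolled by the interim decision. If the extra subjects enter the interval, as 5.3.2 says, the number analysed may be neither 20 nor 37. That too lies outside the sample space, and it affects the 6-cycle interval as well.

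**Step 5: coverage.** An exact interval ordered by stage and count stands in for Duffy-Santner. Over 6-cycle rates of 5%, 10%, 15% and 20% and gains of 0, 2 and 5 points, its coverage of p12, given that it exists, is 0.957-0.991 at nominal 95% and 0.900-0.973 at nominal 90%. The one clear shortfall is at nominal 90% with a 6-cycle rate of 5% and a 10-point gain: 0.855.

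A Clopper-Pearson interval on the 12-cycle count exists for every outcome. At nominal 95%, under the same 6-cycle stopping rule, its coverage is 0.960-0.992 over the rates and gains in the table from 5% to 20%. Over rates of 2-40% and gains of 0-15 points in one-point steps, it is 0.949-0.995.

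**The case against.** A reader might infer that the trial will lack its 12-cycle interval in a sizeable share of cases. The documents do not support that. The larger shares need a true 6-cycle rate near 5-10% together with several points of late response, and no 12-cycle rate is given. At the 20% target the share cannot exceed 7%.

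The evidence for late response is also thin. Section 1.2 reports responses at up to 9 months in the dose-finding study, but five of its seven responders responded only after a dose change that followed three cycles, so the range does not measure late first response on this trial's fixed schedule. The lenalidomide-prednisone study reports responses at up to 32 weeks (224 days, beyond 168), but that is another drug. Non-responders may leave the study at 6 months (3.1), which would lower the gain. All of this stands: late response is possible, and its size is unknown.

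A reader might also infer that intervals will be seriously too narrow. Step 5 does not show that for gains up to 5 points. Those figures belong to a stand-in, since the plan does not describe the named method's construction.

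Finally, after an early stop the regimen has already been declared inactive, and nothing is decided on the 12-cycle rate. That stands too, and it keeps the point minor. It does not remove the mismatch: the plan names a method for an outcome that the method cannot handle.

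**Conclusion.** The point holds in a limited form. The two-stage interval does not apply to the 12-cycle count, because stopping is decided on a different, never larger, count. The stated interval is undefined if the combination cohort stops at stage 1 and reaches 2 or more 12-cycle responders. How often depends on an assumed late gain: from 0 with no gain to 34% (5-point gain) or 56% (10-point gain) at a 6-cycle rate of 5%, and from 0 to about 6% for the same range of gains at the 20% target.

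These shares rest on 20 subjects at an early stop and on independent responses. Continued enrolment makes the first assumption doubtful, and adds a second way for the data to fall outside the sample space. This is a small, cheap correction to a descriptive secondary estimate, not a threat to the trial's conclusion.

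**What to change.** In 5.3.3, replace the interval sentence for the 12-cycle endpoint with wording such as: the 12-cycle response rate will be reported for each cohort with an exact binomial (Clopper-Pearson) 95% confidence interval over all evaluable subjects of that cohort, as a descriptive estimate. Keep Duffy-Santner for the 6-cycle rate only, computed on the 20 or 37 subjects of the decision set. A matching clause is needed in the over-accrual bullet of 5.3.2, so that additional subjects do not enter the Duffy-Santner interval.

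The cost is one sentence and that clause. No sample size, decision rule or data collection changes. The exact interval is usually slightly conservative, with coverage of about 95-99% in the scenarios above.
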